8.1.3 Efficacy population (Parts 1 and 2)

The evaluable population for the secondary efficacy endpoint of ORR will include all patients have received at least one complete cycle of therapy (4 weeks) and have had restaging imaging for response assessment (Section 7.3.5) or been removed for clinical progression. Imaging to confirm progression should be obtained if possible. Patients who are determined ineligible after enrollment or who do not complete at least 1 cycle of therapy (4 weeks) and who do not have a qualifying progression event (radiographic or clinical) (e.g. due to withdrawal of consent or discontinuation due to complications of HCC or underlying liver disease assessed as not related to tumor progression and not treatment-related toxicity) will not be included in efficacy analyses (see Section 5.2.2).

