- 2. Nivolumab will be administered at flat dose of 240 mg IV over 30 minutes every 14 days (-2 to +3 days) on D1 and D15 each cycle starting on C1D1. In Part 2 and with Study Chair approval, patients meeting criteria in Section 6.5 may switch to monthly dosing of nivolumab starting on or after C4D1 (-4 to +6 days) provided no uncontrolled or grade >2 immune related toxicity. A note to file must be included in study chart documenting Study Chair or designee approval. For patients who switch to monthly dosing on or after C4D1, the D15 visit and other assessments may be omitted if not clinically-indicated.
- 3. Cross-sectional imaging with CT or MRI abdomen plus pelvis (including triphasic/multiphase liver) and CT chest with or without contrast is required at screening and every 8 weeks ±14 days until end of treatment; ; at SFFUV1, imaging does not need to be repeated if performed within 28 days prior (±28 day window). Imaging may be performed more frequently if clinically indicated to evaluate for progression or toxicity. RECIST 1.1 measurements should be performed by a radiologist or qualified investigator at each time point.
- 4. Complete blood count and differential (CBCD), metabolic panel including liver and kidney function and electrolytes (see Section 7.3.6 for individual tests required), and PT/INR should be obtained as standard of care safety monitoring before every nivolumab infusion.
- 5. C1D1 blood tests and urinalysis do not need to be repeated if performed within 3 days before C1D1 during screening.
- 6. Perform on women of childbearing potential only at screening within 28 days, 24 hours prior to each nivolumab infusion (including C1D1), and at safety follow up visits. If urine pregnancy results cannot be confirmed as negative, a serum pregnancy test will be required.

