8.2 Statistical and analytical plans

8.2.1 Primary endpoints

Primary and secondary endpoints will be measured in evaluable patients as defined in Section 8.1.

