8.2.2.2 Rate of irAE for combination overall and in Child Pugh B patients

Safety events assessed by treating investigator and/or Study Chair as being at least possibly Immune-related on nivolumab (irAE) will be summarized based on frequency and proportion of total subjects, by system organ class and preferred term as for overall safety. Rate of irAE in Child Pugh B patients in Part 2 will also be summarized.

8.2.2.3 ORR by RECIST 1.1 for overall study and in Parts 1 and 2 individually

ORR is a key secondary endpoint and will be based on RECIST 1.1⁵ as assessed by local radiographic review. ORR will be analyzed for all efficacy-evaluable patients (Parts 1 and 2 combined) as well as for Part 1 and Part 2 individually. ORR defined as the proportion of subjects with RECIST 1.1-measurable disease at study entry (which is required for eligibility) who have a CR or partial response (PR) using RECIST 1.1 at any time during the main study. Subjects with measurable disease at study entry who have unknown or missing response information will be treated as non-responders.

The ORR of sorafenib was approximately 2% in SHARP trial,² and the ORR of nivolumab as monotherapy was 10.2% in Child Pugh B7-8 patients treated with nivolumab in the Child Pugh B cohort of CheckMate 040.³ The ORR of nivolumab in Child Pugh A patients treated with nivolumab as 1st line therapy in CheckMate 459 was 15%.⁴ Thus, an ORR of at least 15% for the combination of sorafenib plus nivolumab in this study would be an encouraging signal of efficacy, if accompanied by acceptable safety in Child Pugh B patients in Part 2 as defined above, and would warrant consideration of a larger study.

For the overall study population, a sample size of 24 evaluable patients from Parts 1 and 2 combined T will have 83% power with 1-sided alpha of 5% to determine true ORR >15%, using Chi-square tests with 1-sided alpha of 5%.

8.2.2.4 Duration of response (DOR), PFS, and OS for Child Pugh B Expansion Cohort and overall study population

In subjects who achieve PR or CR, DOR is defined as the time from first documented evidence of CR or PR until the first documented sign of disease progression or death. For all patients, PFS will be calculated in months from date of first dose of protocol therapy to date of first documented radiographic and/or clinical disease progression or

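### The 8.1.3 response set leaves out early dropouts without progression and unscanned patients, so the ORR read against 15% can be held or raised but not lowered

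*Combined protocol and SAP*

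**What the plan says.** Section 8.1.3 builds the ORR set in two sentences. The inclusion sentence asks for at least one complete 4-week cycle and that patients "have had restaging imaging for response assessment (Section 7.3.5) or been removed for clinical progression". The exclusion sentence removes ineligible patients and those "who do not complete at least 1 cycle of therapy (4 weeks) and who do not have a qualifying progression event (radiographic or clinical"). Its examples are withdrawal of consent, and complications of HCC or liver disease judged to be neither progression nor treatment-related toxicity.

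Section 8.2.1 adds: "Primary and secondary endpoints will be measured in evaluable patients as defined in Section 8.1". Section 8.2.2.3 opens the same way: "ORR will be analyzed for all efficacy-evaluable patients (Parts 1 and 2 combined"). It then gives the definition, "ORR defined as the proportion of subjects with RECIST 1.1-measurable disease at study entry (which is required for eligibility"), with CR or PR at any time in the main study as the numerator, and a rule for gaps: "Subjects with measurable disease at study entry who have unknown or missing response information will be treated as non-responders". The power statement there refers to "a sample size of 24 evaluable patients from Parts 1 and 2 combined".

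Section 8.2.2.3 also says that an ORR of at least 15%, if accompanied by acceptable Part 2 safety, would be an encouraging signal and would warrant consideration of a larger study. Under the schedules in 7.1, imaging is "required at screening and every 8 weeks ±14 days until end of treatment", so the first restaging scan falls in weeks 6 to 10.

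**The concern.** Every eligible patient has measurable disease at entry. Read alone, the definition and missing-response rule in 8.2.2.3 would count an eligible treated patient who withdraws consent in week 3, unscanned and without progression, as a non-responder. Section 8.1.3 takes that patient out of the denominator. The same happens to a patient who completes cycle 1 but has no scan and no clinical progression: the inclusion sentence is not met. For this second group the loss should be small, because the 30-day safety visit also calls for imaging. It mainly concerns consent withdrawal, or death without progression, before the first scan.

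Removing patients with no recorded response leaves the numerator alone and shrinks the denominator. The direction is therefore known before any data are seen, and it favours the 15% benchmark. Early dropout for reasons other than progression is foreseeable in Part 2, which enrolls only Child Pugh B7-9 patients; 8.1.3 itself names complications of underlying liver disease as a reason.

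**Working it through.** **Where each kind of eligible treated patient falls**

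| Patient | 8.1.3 set | Definition in 8.2.2.3 read alone |
|---|---|---|
| Under 4 weeks, no progression, no scan; consent withdrawn or non-progression, non-toxicity complication | Out | Non-responder |
| Same, but stopped for toxicity | Unclear: fits the general exclusion wording, but the examples are limited to non-toxicity reasons | Non-responder |
| Cycle 1 complete, no scan, no clinical progression | Out (fails the inclusion sentence) | Non-responder |
| Cycle 1 complete, removed for clinical progression, no scan | In, as non-responder | Non-responder |
| Cycle 1 complete, scan unevaluable | In, as non-responder | Non-responder |

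**Inputs.** From the documents: 24 patients overall and 12 in Part 2; a total range of 6-24 (8.4); Part 2 closing at 12 patients or on 30 April 2022 (abstract); the 15% benchmark and the 10.2% ORR for nivolumab in Child Pugh B7-8 (8.2.2.3); a median of 4 months on treatment (4.5.2). Assumed: the numbers of responders r and of exclusions k.

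**Shift in ORR.** With N treated and k excluded patients who have no recorded response, ORR moves from r/N to r/(N − k).
- N = 24, r = 3: 3/24 = 12.5%; k = 1 to 4 gives 3/23 = 13.0%, 3/22 = 13.6%, 3/21 = 14.3%, 3/20 = 15.0%.
- N = 24, r = 4: 4/24 = 16.7%; k = 1 to 4 gives 17.4%, 18.2%, 19.0%, 20.0%. It is above 15% either way.

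**When the reading against 15% changes.** This needs r/N < 0.15 and r/(N − k) ≥ 0.15.
- N = 24: r = 3 needs k ≥ 4; r = 2 needs k ≥ 11; r = 1 needs k ≥ 18.
- N = 12 (Part 2 in full): r = 1 needs k ≥ 6 (1/12 = 8.3% to 1/6 = 16.7%).
- One exclusion suffices at N = 21 (3/21 = 14.3% to 3/20 = 15.0%), N = 14 (2/14 = 14.3% to 2/13 = 15.4%) and N = 7 (1/7 = 14.3% to 1/6 = 16.7%). Such totals are possible because accrual may stop early.

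**Chance of reaching 15%.** Assume an all-treated ORR of 10.2% and that all excluded patients are non-responders. The rate in the 8.1.3 set is then 0.102 × N/(N − k).
- N = 24, all treated: 4 responders are needed (4/24 = 16.7%); P(X ≥ 4 | 24, 0.102) = 0.225.
- N = 24, k = 3: rate 0.1166, n = 21, 4 needed; probability 0.224, about the same.
- N = 24, k = 4: rate 0.1224, n = 20, only 3 needed; probability 0.450.
- N = 21: 0.160 over all treated (4 of 21 needed), against 0.364 with k = 1 (rate 0.1071, 3 of 20 needed).

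The jumps occur where the required number of responders falls by one; between those steps almost nothing changes.

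**How many exclusions are plausible.** No rate is given. If time on treatment is exponential (assumption) with median 4 months = 17.39 weeks, the share off treatment by week 4 is 1 − 0.5^(4/17.39) = 14.7%, or 3.5 of 24. By week 8 it is 1 − 0.5^(8/17.39) = 27.3%, or 6.6 of 24. These figures cover all reasons, including progression, so on this assumption they are ceilings for the exclusions at issue.

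**The case against.** The strongest reply is that the plan does not contradict itself. Sections 8.2.1 and 8.2.2.3 name the evaluable set before the missing-response rule appears, and the power statement uses it again. The rule still has work inside that set: patients removed for clinical progression without a scan, and unevaluable scans. This stands. A reader might infer that the two sections are irreconcilable; the text does not force that. A reader might also infer that unscanned cycle-1 completers belong to no category. They do not: they fail the inclusion sentence and so lie outside the set, although the exclusion sentence does not mention them.

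It is also fair that a prespecified response-evaluable set is a legitimate choice for a secondary, descriptive endpoint in a pilot, and that 15% is a signal, not a pass/fail rule. The intervals are wide: the exact 95% CI is 2.7% to 32.4% for 3/24 and 3.2% to 37.9% for 3/20. At 24 treated, the week-4 ceiling of 3.5 lies below the 4 exclusions needed to change the reading.

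Finally, the plan states evaluable targets, and 5.3.2 replaces patients not evaluable for DLT or safety. Replacement could alter the effect if treated numbers exceed 24 overall or 12 in Part 2; that case is not quantified here. None of these points removes the exclusion or reverses its direction.

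**Conclusion.** The point holds as a weakness in the choice of denominator, not as an outright contradiction. Section 8.1.3 leaves out eligible treated patients whom the ORR definition, on its face, would count as non-responders, and leaves early toxicity discontinuations unclear. Provided that the excluded patients have no recorded response, the exclusion can only hold or raise the ORR compared with 15%, and raises it whenever there is at least one responder. Removal of ineligible patients is a separate matter and can act either way.

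The size is modest and conditional: up to 2.5 percentage points with 3 responders in 24 treated and 4 excluded, with the 15% reading changed only at that fourth exclusion. One exclusion can suffice at 21, 14 or 7 treated. A reader might infer that the plan will generally overstate efficacy; the documents do not support that, because they give no exclusion rate and many combinations leave the reading unchanged. The probabilities rest on the assumed 10.2% and the chosen counts. This is a cheap improvement.

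**What to change.** In 8.1.3 and 8.2.2.3, make the ORR used for the 15% benchmark the proportion among all eligible patients with measurable disease at entry who received at least one dose, with a missing response or no post-baseline scan counted as non-response. Keep the present 8.1.3 set as a sensitivity analysis. Say explicitly whether that set holds early toxicity discontinuations, and that cycle-1 completers with neither scan nor clinical progression are outside it. Report the number and reason for each patient in one set but not the other.

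No new data are needed. The costs are a slightly lower reported ORR in some outcomes and a protocol amendment with the approvals in 9.4. The study is open-label, so the change should be settled before ORR is analyzed, with a note of which responses were already known.

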8.2 Statistical and analytical plans

8.2.1 Primary endpoints

Primary and secondary endpoints will be measured in evaluable patients as defined in Section 8.1.

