2.1 Primary objectives

- 1. Part 1: Escalation Cohort: Maximum tolerated dose (MTD) of sorafenib in combination with standard dose nivolumab with Child Pugh A-B7 liver function
- 2. Part 2: Child Pugh B Expansion Cohort: Safety in patients with Child Pugh B liver function

2.2 Secondary objectives for Parts 1 and 2

- 1. Safety and tolerability of combination overall
- 2. Rate of irAE for combination overall and in patients with Child Pugh B liver function
- 3. Objective response rate (ORR) by RECIST 1.15 for overall study
- 4. ORR by RECIST 1.1 in patients with Child Pugh B liver function
- 5. Duration of response (DOR), progression free survival (PFS), and overall survival (OS) for Escalation Cohort and Child Pugh B Expansion Cohort and overall

2.3 Exploratory objectives for Parts 1 and 2

- Relationship between PBMC immune cell subset frequencies, baseline liver function, and clinical outcomes
- 2. Relationship between PBMC T cell receptor (TCR) clonotype frequency and diversity, baseline liver function, and clinical outcomes
- 3. Tumor tissue immune cell subsets and TCR clonotype frequency and diversity in pre-treatment archival tumor tissue samples

4.

- 5. Tumor and immune cell PD-L1 status in pre-treatment archival tumor tissue samples and relationship to clinical outcomes
- 6. Changes in HBV and/or HCV viral load on treatment
- 7. AFP changes on treatment and relationship to clinical outcomes
- Relationship between clinical outcomes and clinicopathologic features including race/ethnicity, etiology of liver disease including HBV/HCV status, baseline liver function, presence of cirrhosis, macrovessel invasion, extrahepatic spread, site(s) of metastatic disease, prior treatment history including prior radiation and arterial therapies

3. Investigators and other study participants

Principal Investigator: [name]

Associate Professor of Clinical Medicine

University of California, San Francisco (UCSF)

A second study site, University of California, Davis (UCD) was activated after completion of Part 1: Dose Escalation Cohort.

4. Study design

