death from any cause. For patients discontinued from study for other reasons than progression or death (see Section 5.2), PFS will be censored at the date last known to be progression-free. OS is defined as the time from the date of first dose of protocol therapy to the date of death due to any cause. Censoring will be performed using the date of last known contact for those who are alive at the time of analysis.

Median DOR, median PFS and OS will be summarized overall and according to treatment group. Kaplan-Meier medians and quartiles may be provided if data warrant. If data warrant, Kaplan-Meier quartile estimates along with the 95% CI will be calculated. Descriptive summaries including swim lane plots may also be generated depending on results.

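### The evaluability rule in 8.1.3, read with 8.2.1, can drop early non-progression deaths from OS and conflicts with the PFS definition, so both medians can be biased upward

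*Combined protocol and SAP*

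**What the plan says.** Section 2.2 lists these among the secondary objectives: "Duration of response (DOR), progression free survival (PFS), and overall survival (OS) for Escalation Cohort and Child Pugh B Expansion Cohort and overall". Section 8.2.1 then sets one general rule for populations: "Primary and secondary endpoints will be measured in evaluable patients as defined in Section 8.1".

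Section 8.1 defines three sets: DLT, safety and efficacy. The efficacy set in 8.1.3 opens with a single endpoint: "The evaluable population for the secondary efficacy endpoint of ORR will include all patients have received at least one complete cycle of therapy (4 weeks"), with restaging imaging or removal for clinical progression also required. Its last sentence reaches further. Patients found ineligible, or "who do not complete at least 1 cycle of therapy (4 weeks) and who do not have a qualifying progression event (radiographic or clinical"), "will not be included in efficacy analyses (see Section 5.2.2"). The examples given are patients who leave "due to withdrawal of consent or discontinuation due to complications of HCC or underlying liver disease assessed as not related to tumor progression" and not to treatment toxicity. Death is not listed as a qualifying event.

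Section 8.2.2.4 defines the time-to-event endpoints differently. For PFS: "For all patients, PFS will be calculated in months from date of first dose of protocol therapy", ending at progression or at death whatever its cause. Patients who stop for reasons other than progression or death are censored when last known to be progression-free. For OS: "OS is defined as the time from the date of first dose of protocol therapy to the date of death due to any cause". Patients still alive are censored at last contact. No analysis set is named for OS.

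**The concern.** A death is an OS and PFS event by definition. A rule that admits a patient only after four weeks of therapy or a progression event makes entry to the analysis depend partly on having survived. Each early death without progression that it removes can only raise the estimated median.

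The patients at risk of removal are foreseeable. Part 2 enrols Child Pugh B patients, and 8.1.3 itself gives complications of underlying liver disease as an example. With 12 patients expected in Part 2, one or two exclusions change the result visibly. A patient who stops in cycle 1 for such a complication and dies later would also be lost from OS, although 6.10 continues survival follow-up after discontinuation.

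**Working it through.** The plan states no target median, event count or power for PFS or OS, so there is no figure to reproduce. The check has a textual part and an illustration of size.

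**Text.** Take a treated patient who dies on day 20 of liver failure, without progression and not treatment-related.

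- Under 8.2.1 with 8.1.3: cycle 1 not completed and no progression event, so not in efficacy analyses.
- Under 8.2.2.4, PFS: an event at day 20.
- Under 8.2.2.4, OS: an event at day 20, but with no population stated other than the one 8.2.1 points to.

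A patient who withdraws consent in cycle 1 is excluded under 8.1.3 but censored for PFS under 8.2.2.4. Dropping that patient has no fixed direction of bias.

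**Effect of dropping k early deaths from n patients.** Assume exponential survival with median m and let q = k/n. The new median t solves S(t) = 0.5(1 − q), so t/m = 1 − log2(1 − q).

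- 1 of 12: 1 − log2(11/12) = 1.126, or +13%.
- 2 of 12: 1 − log2(10/12) = 1.263, or +26%.
- 1 of 24: 1.061, or +6%.
- 2 of 24: 1.126, or +13%.
- None dropped: 1.000.

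In 200,000 simulated uncensored samples, the ratios of mean sample medians (midpoint convention) were 1.11, 1.25, 1.06 and 1.12 in the same order. With the Kaplan-Meier step convention (first time S ≤ 0.5), dropping one death gave 1.26 at n = 12 and 1.12 at n = 24.

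**How likely is an early death?** The medians are assumptions, taken from figures quoted in 1.3.2 (4.2, 6.5 and 9.2 months) and 1.4.2 (15.0 months). With 28 days = 28/30.4375 = 0.92 month, P(death within 28 days) = 1 − 2^(−0.92/m). The chance of at least one among 12 is 1 − (1 − P)^12. The last column sets q to between 25% and 100% of P.

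| Assumed median OS (months) | P(death within 28 days) | At least one of 12 | Rise in median if 25% to 100% of these deaths are dropped |
|---|---|---|---|
| 4.2 | 14.1% | 84% | 5% to 22% |
| 6.5 | 9.3% | 69% | 3% to 14% |
| 9.2 | 6.7% | 57% | 2% to 10% |
| 15.0 | 4.2% | 40% | 1.5% to 6% |

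The 100% figures are ceilings, since only deaths without progression can be dropped.

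**A lower anchor.** Appendix 3 lists 80% one-year survival for Child Pugh B. It describes liver function classes, not advanced HCC, so it is only a rough guide to liver-related death. At a constant hazard, 1 − 0.8^(28/365) = 1.7% by day 28, or 12 × 0.017 = 0.2 patients. If all were dropped, the ratio is 1 − log2(1 − 0.017) = 1.025, or +2.5%.

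**The case against.** The strongest reply is that the specific rule should override the general one. Section 8.1.3 is introduced for ORR, and its requirements concern response evaluation. Section 8.2.2.3 ties ORR to efficacy-evaluable patients by name, while 8.2.2.4 does not do so for PFS or OS. The PFS text speaks of all patients and censors the kind of early discontinuation that 8.1.3 would exclude. The OS text has deaths and censored survivors and no third category. On this view the plan already intends all treated patients.

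That is a fair reading and it stops the point from being stated flatly. It does not settle the matter. The PFS phrase may only contrast PFS with DOR, which applies to responders alone. For OS there is no such phrase. The closing sentence of 8.1.3 is not confined to ORR, and 8.2.1 covers every secondary endpoint.

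Other limits stand. Entry criteria reduce early liver death: ECOG 0 or 1, no paracentesis or hospitalisation for encephalopathy within 6 months, and no variceal bleed within 12 months. No decision rests on PFS or OS; the signal for a larger study is ORR with acceptable safety. At n = 12 the uncertainty of a median is large in any case.

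**Conclusion.** The point holds as a conflict in the plan that can bias the result. For OS, the only rule that supplies a population allows treated patients who stop or die within four weeks without progression to be left out. For PFS, the same rule contradicts the endpoint's own definition. If such deaths occur and are dropped, the median rises by about 13% for one of 12 and 26% for two of 12, assuming exponential survival. If none occurs, there is no upward bias by this route.

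A reader might infer more than the documents support:

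- That both medians are biased as the plan stands. This depends on which passage the analyst follows and on whether such deaths occur.
- That all early deaths are removed. Those with radiographic or clinical progression stay in. Treatment-related deaths are unclear: the main clause of 8.1.3 would drop them, but its examples describe only causes that are not treatment-related.
- That non-tumour liver death is the main competing risk. The documents do not say so.
- That this rule makes the combination look safer. Safety is analysed in the 8.1.2 set, whose own exclusion is a separate matter.

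Severity is moderate: these are descriptive secondary endpoints in a pilot study.

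**What to change.** - In 8.1.3, limit the evaluability rule and its closing exclusion to ORR.
- In 8.1.3 and 8.2.2.4, state that PFS and OS are analysed in all patients who received at least one dose of study drug, from first dose, with every death an event whenever it occurs.
- Amend 8.2.1 so that its general sentence agrees.

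This takes a few sentences and no new data, since survival follow-up already continues after discontinuation. The downside is that reported medians may be slightly shorter. The change should be made before the data are analysed, so that the denominator is not chosen once the early deaths are known.
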